#### **5.12.1.2. The Analysis Relative to the Treatment-Regimen Estimand**

The analysis will be conducted utilizing HbA1c data in FAS at baseline and at the 52-week visit with the aid of an Analysis of Covariance (ANCOVA). The response variable will be the primary measure and model terms will include treatment, country/pooled country, SGLT2 inhibitor use at baseline as fixed effects, and baseline HbA1c as a covariate. The ANCOVA analysis will be conducted with multiple imputation of missing primary measure (see Section 5.12.1.3 for details) and statistical inference over multiple imputation of missing data guided by Rubin (1987).

With the aid of the ANCOVA analysis, 2-sided 97.5% CI for mean change in HbA1c from baseline to 52-week visit for (10mg tirzepatide – insulin glargine) as well as for (15mg tirzepatide – insulin glargine) will be derived. If the upper limits of the CI are  $\leq 0.3\%$ , then the respective dose of tirzepatide (10mg and/or 15mg) will be declared noninferior to insulin glargine relative to change in HbA1c from baseline.

#### **5.12.1.3. Methods for Multiple Imputations**

For efficacy analysis relative to “treatment-regimen” estimand, missing HbA1c data at the 52-week visit will be imputed based on “retrieved dropouts,” defined as patients who had their HbA1c value measured at the 52-week visit in the same treatment arm who prematurely discontinued study drug. If the imputed value of HbA1c change from baseline is  $< -6.0\%$  or  $> 6.0\%$ , that value will be set to  $-6.0\%$  or  $6.0\%$ , respectively, to avoid unrealistic imputed values.

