For the FDA, the primary efficacy assessments will be guided by the “treatment-regimen” estimand. This assessment will analyze change from baseline in HbA1c to 52-week visit using an analysis of covariance (ANCOVA) with terms, treatment, stratification factors: country, SGLT-2i use (Yes or No), and baseline HbA1c as a covariate. The ANCOVA analysis will be conducted using full analysis set (FAS) at 52-week visit, which consists of all available change from baseline in HbA1c data at the 52-week visit, irrespective of whether they were obtained while the participants had discontinued the study drug or whether the participant had been given rescue medication. Additionally, data for subjects with missing values will be imputed based on observed data from subjects in the same treatment arm who had their efficacy measure at the Week 52 visit assessed after early discontinuation of study drug and/or initiation of rescue medication (retrieved dropouts). Analysis will be conducted with multiple imputations, and statistical inference over multiple imputations will be guided by the method proposed by Rubin (1987).

For all other purposes, the primary efficacy assessments will be guided by the “efficacy” estimand. This assessment will use efficacy analysis set (EAS) which consists of data obtained before the initiation of any rescue therapy and before premature treatment discontinuation. The analysis model for change from baseline in HbA1c assessed over time will be a mixed model for repeated measures (MMRM), with terms: treatment, visit, and treatment-by-visit interaction, stratification factors: country, SGLT-2i use (Yes or No), as fixed effects, and baseline HbA1c as a covariate. An unstructured covariance structure will model relationship of within-patient errors.

Since the two estimands are intended for different purposes, no multiplicity adjustments will be made. For each estimand, the overall type I error rate of primary and key secondary efficacy endpoint assessments relative to each estimand will be controlled at 2-sided 0.05 level.

Additional details, including analysis methods for key secondary endpoints and the strategy for controlling overall type 1 error rate in evaluating primary and key secondary endpoint evaluation to a 2-sided 0.05 significance level, will be provided in the statistical analysis plan (SAP).

Safety Analyses:

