10.3.3. Efficacy Analyses

10.3.3.1. Primary Analyses

As indicated in Section 10.3.1, there will be 2 primary efficacy analyses conducted to establish noninferiority of 10 mg LY3298176 and 15 mg LY3298176 to insulin glargine relative to mean change in HbA1c from baseline to 52-week visit.

For the FDA, the primary efficacy analysis will be guided by the “treatment-regimen” estimand defined in Section 10.3.1. This assessment will analyze change in HbA1c values obtained at 52-week visit using an analysis of covariance (ANCOVA) with terms, treatment, stratification factors, and baseline HbA1c as a covariate. Missing change in HbA1c from baseline values at 52-week visit will be imputed based on observed changes in HbA1c from baseline values at the visit from patients in the same treatment arm who had their efficacy assessed after early discontinuation of study drug and/or initiation of rescue antihyperglycemic medication. With the aid of the ANCOVA, 2-sided 97.5% CI for the difference in mean change in HbA1c from baseline to 52-week visit between 10 mg LY3298176 and insulin glargine as well as between 15 mg LY3298176 and insulin glargine will be constructed. Analysis will be conducted with multiple imputations, and statistical inference over multiple imputations will be guided by the method proposed by Rubin (1987). If the upper limit of the CI is below 0.3%, LY3298176 dose will be declared noninferior to insulin glargine.

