### Revision History

SAP Version 1 was approved prior to the first patient receiving study drug.

SAP version 2 was approved prior to the interim cardiovascular (CV) meta-analysis and final database lock. The main changes of this version are:

1. Updated definition of analysis set: Per agreement with the US Food and Drug Administration (FDA), patients that discontinue study drug due to inadvertent enrollment are excluded from efficacy analyses.
2. Updated baseline definition for selected measures based on scientific consideration and to minimize missing values at baseline.
3. Updated primary endpoint: Missing data imputation. Corrected the definition of “retrieved dropout.” Use of local laboratory data for glycemic control measures when central laboratory data are not available.
4. Updated the language to handle lack of convergence in longitudinal logistic regression analysis due to low number of events for hemoglobin A1c (HbA1c) and weight loss target analyses.
5. Updated the language in section on adverse events of special interest and renamed section to “Special Safety Topics” to be consistent with the program SAP (see Section 5.13.2).
6. Updated the language in Section 5.13.2.1 to provide clarity on definitions of different categories of hypoglycemic events and analysis of hypoglycemic events.
7. Added Section 5.13.3 for additional analyses on renal safety based on a revised definition of renal impairment (eGFR<60 mL/min/1.73m^2 or UACR >300 mg/g at baseline).
8. Added language in Section 5.19.1 according to protocol amendment (b) for an interim data extraction to support the program wide interim cardiovascular safety meta-analysis.
9. Added Section 5.20 for COVID-19 impact assessment.

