### **Study Period III (variable treatment period)**

Long-term safety period (Visit 25 to Visit 29):

Some patients will continue to receive tirzepatide or insulin glargine for up to, but not longer than, 24 months, as determined by the sponsor.

When the sponsor determines that the study completion criteria have been met, all patients will return to the site for a final treatment visit (FTV) within approximately 30 days. Patients who attend Visit 29 (24 months) or the FTV are considered to have completed the treatment period.

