### 5.10.1. Exposure and Compliance to Tirzepatide

Number of patients prematurely discontinuing study treatment prior to the 52-week visit as well as before the end of efficacy follow-up will be provided by study treatment. Reasons for prematurely discontinuing study treatment prior to the 52-week visit as well as before the end of efficacy follow-up will be provided by study treatment. Time-to-event analysis of premature study treatment discontinuation will be conducted.

Proportion of patients with missing dosing information, receiving no tirzepatide dose, receiving 2.5mg, 5mg, 7.5mg, 10mg, 12.5mg or 15mg will be presented by randomized treatment and week from first dose.

Listing and summary of patients continuing on a reduced maintenance dose of tirzepatide compared to the randomized dose may be provided.

The compliance will be defined as taking at least 75% of the scheduled tirzepatide doses. Compliance will be calculated by taking the number of doses administered (regardless the actual dose administered) divided by the total number of doses expected to be administered  $\times 100$ . Treatment compliance will be summarized descriptively over the entire study period by treatment using the mITT population.

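### SAP 5.12.1.3 does not require retrieved dropouts to have stopped study drug before Week 52, so the rule as written admits on-drug Week 52 values as donors

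*SAP*

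**What the plan says.** SAP 5.12.1.3 fills in missing Week 52 HbA1c for the treatment-regimen estimand from retrieved dropouts: "patients who had their HbA1c value measured at the 52-week visit in the same treatment arm who prematurely discontinued study drug". That gives three conditions: same arm, a Week 52 value, and premature discontinuation. None says when the drug was stopped. SAP 5.12.2.3 (HbA1c <7%) refers to the same method. SAP 5.12.2.2 (body weight) follows it by analysing weight in the manner of the primary analysis.

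Protocol 10.3.3.1 does state the order. Its donors are patients in the same arm "who had their efficacy assessed after early discontinuation of study drug and/or initiation of rescue antihyperglycemic medication". The Protocol Synopsis, which attaches the label retrieved dropouts, and Protocol 10.3.3.2 say the same in substance.

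Two other parts of the SAP bear on the meaning of premature:

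- Study Period III: "Some patients will continue to receive tirzepatide or insulin glargine for up to, but not longer than, 24 months", and "Patients who attend Visit 29 (24 months) or the FTV are considered to have completed the treatment period".
- SAP 5.10.1 tabulates "Number of patients prematurely discontinuing study treatment prior to the 52-week visit as well as before the end of efficacy follow-up".

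**The concern.** Because completion means reaching Visit 29 or the final treatment visit, a stop between Week 52 and that point is premature. SAP 5.10.1 shows that where the SAP wants a Week 52 limit, it writes one; 5.12.1.3 does not. The full analysis set offers no protection, because SAP Table GPGM.5.1 includes Period III data. A programmer who flags donors from the disposition records would be following the SAP and would still include patients whose Week 52 HbA1c was measured on drug.

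Two things are at stake. First, the donor pool stands in for patients who left, and an on-drug value does not describe an off-drug outcome. Second, donor status would depend on what happens after Week 52. Two patients with identical histories up to that visit would be classed differently according to later events, in a period whose length varies between patients. A Week 52 estimate should not depend on that.

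**Working it through.** **The texts compared.**

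| Condition on the donor | Protocol 10.3.3.1 | SAP 5.12.1.3 |
|---|---|---|
| Same arm | yes | yes |
| Week 52 value observed | yes | yes |
| Value taken after the drug was stopped | yes | not stated |
| Rescue also qualifies | yes | not stated |

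Consider a patient on drug at Week 52 who stops at Week 70. Under the SAP conditions this patient is a donor. Under the protocol conditions the patient is not, unless rescue began before Week 52.

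**The plan's own figure.** Protocol 10.1 gives 90% power for 313 versus 939 patients, a difference of 0.30%, an SD of 1.3% and two-sided alpha of 0.025.

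- SE = 1.3 × √(1/313 + 1/939) = 0.085%.
- The calculated power is 90.2%, so the stated figure reproduces. It does not use the donor definition, so changing the definition leaves planned power and sample size as they are.

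**Size of the effect.** Let m be the share missing at Week 52, q the share of donors who stopped only after Week 52, and g the gap in mean HbA1c change between off-drug and on-drug patients.

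- Shift in donor mean = q × g
- Shift in arm mean = m × q × g

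The documents give none of these rates; all values below are assumptions.

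*Central illustration, 313-patient tirzepatide arm.* Suppose 8% stop before Week 52 and have a Week 52 value (25 patients), and 4% stop later (13 patients).

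- q = 13/(25 + 13) = 0.34
- Donor mean, g = 1.0-1.5%: 0.34 × 1.0 = 0.34% to 0.34 × 1.5 = 0.51%
- Arm mean, m = 5-10%: 0.05 × 0.34 = 0.017% to 0.10 × 0.51 = 0.051%

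*Is a third plausible?* Protocol 10.1 expects average follow-up of 18 to 22 months, so 6 to 10 months fall after Week 52. If stopping were spread evenly over time and every early stopper were retrieved, later stops would be 6/18 = 33% to 10/22 = 45% of the pool. Front-loaded stopping lowers the share; early stoppers without a Week 52 value raise it.

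*Wider range.* With 5-10% true retrieved dropouts (16-31 patients) and 2-10% stopping in Period III (6-31 patients), q runs from about 0.17 to 0.67. With g = 0.5-1.5% and m = 5-10%, the arm mean moves from 0.05 × 0.17 × 0.5 = 0.004% to 0.10 × 0.67 × 1.5 = 0.10%.

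**Net effect on the treatment difference.** Assume a smaller glargine gap of 0.3-0.5% and the same q. The glargine arm then moves 0.05 × 0.34 × 0.3 = 0.005% to 0.10 × 0.34 × 0.5 = 0.017%.

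- Equal missingness in both arms: 0.05 × 0.34 × (1.0 − 0.5) = 0.01% to 0.10 × 0.34 × (1.5 − 0.3) = 0.04%, favouring tirzepatide.
- Tirzepatide 5% missing with g = 1.0, glargine 10% missing with g = 0.5: 0.017 − 0.017 = 0.
- As in the last case, but with half the glargine donors on drug: 0.017 − 0.10 × 0.5 × 0.5 = −0.008%, so the sign reverses.

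**The case against.** The strongest reply is that the intended meaning is clear. The label itself, and the protocol's statement that the value is assessed after discontinuation, both point to patients who were off drug at Week 52. SAP 5.2 says that changes to protocol methods will be described with a justification, and no decision to admit later stoppers is described. This stands as far as intent goes: the wording permits on-drug donors, but nothing shows that the analysis will be programmed that way. It does not rescue the text, because the SAP gives its own explicit definition, and that definition conflicts with the protocol's.

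Three stronger readings are tempting, and the documents do not support them.

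- A reader might infer that SAP version 2 removed the order. The Revision History says only "Missing data imputation. Corrected the definition of" the retrieved dropout. Version 1 is not available, so what changed cannot be established.
- A reader might infer a bias in favour of tirzepatide. As shown in the working, that needs similar missingness and donor shares in the arms as well as a larger tirzepatide gap. None of these is in the documents.
- A reader might infer that the imputed values are necessarily too favourable. That holds only if the missing patients are mainly off drug. SAP 5.12.1.3 imputes all missing Week 52 values from this pool, and SAP 5.20.4 anticipates primary endpoint visits missed because of COVID-19. For a patient who missed the visit while still on drug, an on-drug donor is the closer match.

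It is also fair to say that the effect is small against an SE of 0.085%.

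**Conclusion.** The point holds as a defect in a stated rule for the primary FDA analysis. Followed literally, SAP 5.12.1.3 admits on-drug Week 52 values, contradicts the protocol, and makes a Week 52 result depend on later events.

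If on-drug values are better and missing patients are mainly off drug, each arm's imputed values are pulled towards its on-drug mean. Under the central assumed rates, a tirzepatide arm mean moves about 0.02-0.05%, which is roughly 6-17% of the 0.3% margin and 0.2-0.6 of the SE. The net shift in the treatment difference is probably smaller, its direction is open, and it is unlikely to reverse the primary conclusion. The composition of a small donor pool could nevertheless change substantially. Confidence is high on the wording and low on size and direction, because every rate is assumed.

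**What to change.** Reword SAP 5.12.1.3 so that retrieved dropouts are patients in the same arm who permanently discontinued study drug before the 52-week visit and whose 52-week value was measured after that discontinuation. Define after with a stated cut. Last dose date plus 7 days, already the data cut for the efficacy analysis set, is one option, although the SAP gives no basis for it as an off-drug criterion for HbA1c.

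Apply the same definition to body weight (5.12.2.2) and HbA1c <7% (5.12.2.3). In the same edit, reconcile with the protocol whether patients who started rescue are also donors; correcting the timing alone leaves that difference open.

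The cost is a sentence or two in the SAP before database lock. The timing condition makes the donor pool smaller, and the standard error may be slightly larger. Planned sample size and power do not change.

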#### **5.12.1.4. Additional Analyses of the Primary Outcome**

Upon successfully establishing noninferiority of tirzepatide compared to insulin glargine, superiority of tirzepatide compared to insulin glargine relative to change in HbA1c from baseline will be evaluated (see Section 5.12.3).

### **5.12.2. Secondary Efficacy Analyses Subject to Type 1 Error Rate Control**

#### **5.12.2.1. Mean change in HbA1c from baseline at the 52 week visit**

Noninferiority of 5mg tirzepatide to insulin glargine will be conducted in a manner similar to Section 5.12.1. Assessment of Superiority of tirzepatide doses compared to insulin glargine will be conducted using the same statistical models as those used for evaluating the primary objective in Section 5.12.1. Decisions will be guided by the two-sided p-values for mean comparisons between tirzepatide doses and insulin glargine (see details in Section 5.12.3).

#### **5.12.2.2. Mean change in body weight from baseline at the 52 week visit**

The analysis for change in body weight from baseline (postbaseline - baseline) will be conducted in a manner similar to the primary analysis in Section 5.12.1. Baseline HbA1c concentration ( $\leq 8.5\%$ ,  $> 8.5\%$  [ $\leq 69$ ,  $> 69$  mmol/mol]) will be used as a fixed factor in place of baseline HbA1c as a covariate and baseline body weight will be used as an additional covariate in the statistical

model. Least Squares Mean (LSM) estimate of mean change in body weight from baseline will be plotted by nominal visit and by study treatment. For multiple imputation of missing values, if the imputed value of weight change from baseline is  $<-50$  kg or  $>50$  kg, then that value will be set to  $-50$  kg or  $50$  kg, respectively, to avoid unrealistic imputed values.

### **5.12.2.3. Proportion of Patients Achieving HbA1c $<7\%$ at the 52 week Visit**

The analysis relative to the “efficacy” estimand for the endpoint at 52 weeks will be conducted using EAS with missing values imputed from an MMRM model and then dichotomized. The MMRM model includes country/pooled country, SGLT2 inhibitor use at baseline, treatment, visit, and treatment-by-visit interaction as fixed effects, and baseline HbA1c as a covariate. After dichotomizing continuous HbA1c, the data is analyzed using a logistic regression model with treatment, country/pooled country, SGLT2 inhibitor use at baseline, and baseline HbA1c as a covariate. In addition, analysis will be conducted utilizing data using EAS from baseline through the 52-week visit with the aid of a longitudinal logistic regression with repeated measurements with country/pooled country, SGLT2 inhibitor use at baseline, treatment, visit, treatment-by-visit interaction as fixed effects, and baseline HbA1c as a covariate. In the case that longitudinal logistic model does not converge due to small number of events, logistic regression will be utilized to analyze proportion of patients achieving HbA1c $<7\%$  at nominal visits.

Analysis relative to “treatment-regimen” estimand will be conducted utilizing HbA1c data in FAS at baseline and at the 52-week visit with the aid of a logistic regression with multiple imputation of missing HbA1c data at the 52-week visit (see Section 5.12.1.3 for details). Model terms will include treatment, country/pooled country, SGLT2 inhibitor use at baseline as fixed effects, and baseline HbA1c as a covariate and statistical inference over multiple imputations will be guided by Rubin (1987).

[figure not shown]

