10.3.3.2. Secondary Analyses

The secondary study objectives subject to type 1 error rate control are as follows:

- noninferiority of 5 mg LY3298176 dose to insulin glargine relative to mean change in HbA1c from baseline to 52-week visit
- superiority of each LY3298176 dose to insulin glargine relative to mean change in HbA1c from baseline to 52-week visit
- superiority of each LY3298176 dose to insulin glargine relative to mean change in body weight from baseline to 52-week visit
- superiority of each LY3298176 dose to insulin glargine relative to proportion of patients achieving target value of HbA1c <7% at 52-week visit

Type 1 error-controlled strategy for primary and secondary endpoints will be described in the SAP. All type 1 error-controlled secondary efficacy analyses will be conducted relative to both estimands, the “efficacy” estimand and the “treatment-regimen” estimand.

Analysis of change from baseline in body weight at 52-week visit will be conducted in a manner similar to the primary efficacy analyses with change in body weight from baseline as the response variable, baseline HbA1c category ($\leq 8.5\%$, $> 8.5\%$) in place of baseline HbA1c, and baseline body weight as a covariate.

Comparisons among treatments relative to proportion of patients achieving HbA1c target value of <7.0% (53 mmol/mol) at 52-week visit will be conducted using a logistic regression analysis with terms treatment, country, SGLT-2i use (Yes or No), and baseline HbA1c as a covariate. In the analysis of patients achieving HbA1c target value relative to the “efficacy” estimand, subjects with missing values at 52-week visit will be excluded. In the analysis of patients achieving HbA1c target value relative to the “treatment-regimen” estimand, missing values at 52-week visit will be imputed based on observed data at respective visits from patients in the same treatment arm who had their efficacy assessed after early discontinuation of study drug and/or initiation of rescue medication. Analysis will be conducted with multiple imputations and statistical inference over multiple imputations will be guided by the method proposed by Rubin (1987).

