### 5.4. Handling of Dropouts or Missing Data

For the primary and key secondary efficacy endpoint analyses subject to type 1 error rate control, data for patients with missing values at the 52-week visit will be imputed based on the method describe in Section 5.12.1.3. Unless specified otherwise, imputation of missing data will be limited to primary and key secondary efficacy endpoint analysis. Missing other secondary or exploratory efficacy parameter values and missing safety laboratory values will not be explicitly imputed.

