## 5.12. Efficacy Analysis

For the FDA and potentially for other regulatory agencies, all efficacy assessments will be guided by the “treatment-regimen” estimand conducted using FAS. Assessment of the primary and secondary efficacy objectives subject to type 1 error rate control (key secondary) will be conducted with multiple imputation of missing data (see Section 5.12.1.3) at 52 weeks.

Assessment of other efficacy objectives will be conducted without imputation of missing data. For publications and other purposes, the assessment of efficacy objectives will be guided by the “efficacy” estimand using EAS set without imputation of missing data. A listing of patients randomized but not included in efficacy analyses (ie, not treated, discontinued treatment due to inadvertent enrollment) will be provided.

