**Figure GPGM.5.1. Type 1 Error control strategy for primary and key secondary efficacy endpoints.**

#### 5.12.4. Other Secondary and Exploratory efficacy Analyses

Other secondary and Exploratory efficacy measures will be summarized by treatment and nominal visit. Statistical analyses will be conducted in a manner similar to Sections 5.12.1 and 5.12.2. However, missing data will not be imputed and assessments are not subject to type 1 error rate control.

Objective	Relative to the efficacy measure:	Analysis Conducted in a manner similar to:	Additional Information
QW tirzepatide 5 mg, 10 mg, and/or 15 mg is superior to insulin glargine at 52 weeks	Change from baseline in fasting serum glucose	5.12.1	Use baseline HbA1c strata as a fixed effect in place of baseline HbA1c as a covariate. Use baseline FSG as a covariate. LSM estimates will be plotted by treatment and visit.
	Change from baseline in 7-point self-monitored blood glucose (SMBG) profiles	5.12.1	Use baseline HbA1c strata as a fixed effect in place of baseline HbA1c as a covariate. Use baseline SMBG as a covariate. LSM estimates at 52-weeks will be plotted by treatment and 7-points.
	proportion of patients achieving an HbA1c target value of $\leq 6.5\%$ (48 mmol/mol),	5.12.2.3	None
	proportion of patients achieving an HbA1c target value of $< 5.7\%$ (39 mmol/mol).	5.12.2.3	None
	proportion of patients who achieved weight loss of $\geq 5\%$ , from baseline	5.12.2.3	Use baseline HbA1c strata as a fixed effect in place of baseline HbA1c as a covariate and baseline weight as a covariate
	proportion of patients who achieved weight loss of $\geq 10\%$ from baseline	5.12.2.3	Use baseline HbA1c strata as a fixed effect in place of baseline HbA1c as a covariate and baseline weight as a covariate
	proportion of patients who achieved weight loss of $\geq 15\%$ from baseline	5.12.2.3	Use baseline HbA1c strata as a fixed effect in place of baseline HbA1c as a covariate and baseline weight as a covariate
To compare tirzepatide 5 mg, 10 mg, and 15 mg to insulin glargine at 52 weeks	Change from baseline in waist circumference	5.12.1	Use baseline HbA1c strata as a fixed effect in place of baseline HbA1c as a covariate. Use baseline waist circumference as a covariate.
	Change from baseline in lipid parameters (Total-Cholesterol, HDL, VLDL, TG)	5.12.1	Use baseline HbA1c strata as a fixed effect in place of baseline HbA1c as a covariate. Use corresponding

			baseline lipid parameter as a covariate.

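### For HbA1c <7% under the efficacy estimand, the SAP both rules out and requires imputation, and gives no draw method or combining rule for the imputation it requires

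*SAP*

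**What the plan says.** HbA1c <7% at Week 52 is a key secondary objective under strong type 1 error control (SAP 3.2). Protocol 10.3.3.2 requires such objectives to be analysed under both estimands. For the efficacy estimand, the documents give these rules on missing data:

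- **SAP 5.12:** objectives are assessed under the "estimand using EAS set without imputation of missing data". The sentence carries no exception.
- **SAP 5.12.2.3:** the analysis is "conducted using EAS with missing values imputed from an MMRM model and then dichotomized", followed by a logistic regression on treatment, country, SGLT2 inhibitor use and baseline HbA1c. A second model follows: "In addition, analysis will be conducted utilizing data using EAS from baseline through the 52-week visit with the aid of a longitudinal logistic regression". The text does not say which of the two enters the testing sequence in 5.12.3.
- **Protocol 10.3.3.2:** "subjects with missing values at 52-week visit will be excluded".
- **SAP 5.4:** for primary and key secondary analyses, "data for patients with missing values at the 52-week visit will be imputed based on the method describe in Section 5.12.1.3", without distinguishing estimands. SAP 5.12.1.3 itself covers only the treatment-regimen estimand.
- **SAP 5.12.4:** sends the other HbA1c and weight-loss targets to 5.12.2.3 and adds "However, missing data will not be imputed and assessments are not subject to type 1 error rate control".

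Multiple imputation and Rubin's rules do appear in 5.12.2.3, but only in the next paragraph, which concerns the treatment-regimen estimand.

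**The concern.** There are two faults. First, 5.12 and 5.12.2.3 give opposite instructions for the same endpoint, estimand and data set. For a logistic model at a single visit, no imputation amounts to the protocol's exclusion rule, so the choice is between dropping patients and filling in their values.

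Second, even if 5.12.2.3 governs, it is incomplete. Read literally, it produces one completed dataset and one logistic fit. Imputed values then count as observed, and standard errors are too small. If the imputed values are MMRM predictions, they also vary less than real HbA1c values, so dichotomising them at 7% distorts the responder rates.

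At stake are the significance call, the confidence interval and the responder difference for a controlled endpoint. They would be reported under the estimand that SAP 5.12 assigns to publications and other purposes outside the FDA review. The trial is open-label, so this choice should be closed in advance.

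**Working it through.** **Which rule applies.** SAP 5.12.2.3 is specific to the endpoint and estimand, so it looks intended, and 5.12 lacks the matching exception. The wording of 5.12.4 fits this reading but is weak support, because the sections it cites also contain treatment-regimen imputation. SAP 5.4 does not fill the gap, because the method it points to is confined to the other estimand.

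**Inputs from Protocol 10.1.** 313 patients per tirzepatide arm and 939 on glargine; mean difference 0.30%; SD 1.1%; at most 28% starting rescue or stopping study drug by Week 52. The plan states no figure for HbA1c <7%. The stated power above 90% for mean HbA1c under this estimand reproduces from these inputs. With 72% retained, SE = 1.1 × √(1/676.08 + 1/225.36) = 0.0846, and power = Φ(0.30/0.0846 − 2.241) = 90.4%. At 28%, about 88 of 313 values per tirzepatide arm (0.28 × 313 = 87.6) and 263 of 939 glargine values (0.28 × 939 = 262.9) would be imputed or excluded.

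**Assumptions not in the documents.** SD 1.1% also applies to the Week 52 value; 10% missing as a milder case; arm means from 6.0 to 7.5%; correlation of the last on-treatment value with Week 52 of 0.3, 0.5 or 0.7; baseline correlated 0.3 with the last value and 0.2 with Week 52; dropout unrelated to HbA1c.

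**Simulation.** Logistic model on treatment and baseline HbA1c (country and SGLT2 inhibitor use omitted). Imputation regression on treatment, baseline and last value. Multiple imputation used 20 imputations with parameter and residual draws. There were 24 scenarios with equal means (5000 trials each) and 24 with a difference of 0.30 (4000 trials each).

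*Different calls at p<0.05, true difference 0.30:*

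| Comparison | 28% missing | 10% missing |
|---|---|---|
| Exclusion vs multiple imputation | 5–11% of trials | 2–5% |
| Exclusion vs predicted values | 8–17% | 4–7% |

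*Calibration with 28% missing (SE ratio and coverage at difference 0.30, false positives at equal means):*

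| Method | Reported SE / true SD | 95% CI coverage | Ungated false positives at nominal 5% |
|---|---|---|---|
| Exclusion | 0.98–1.01 | 94–96% | 4.8–5.2% |
| Multiple imputation, Rubin's rules | 1.07–1.13 | 96.5–97.6% | 2.4–3.3% |
| One random draw | 0.84–0.92 | 90–93% | 6.9–9.4% |
| Predicted values | 0.63–0.94 | 76–93% (corr. 0.5–0.7); 47–94% (0.3) | 6.5–14.0% (corr. 0.5–0.7); 5.2–23.3% (0.3) |

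With 10% missing, coverage is 93–95% with one draw and 84–95% with predicted values.

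*Gated result.* If the same dose must first show HbA1c superiority at two-sided 0.025, false rejection in favour of the drug is at most 1.2% with any method. That order is inferred, because the SAP's testing figure is not reproduced in the text. The weight and 5 mg gates were not modelled.

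**Responder difference with predicted values (closed formula, no baseline covariate).** Predictions have SD 1.1r instead of 1.1, where r is the correlation and q the missing share:

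(1−q)·[Φ((7−m1)/1.1) − Φ((7−m0)/1.1)] + q·[Φ((7−m1)/(1.1r)) − Φ((7−m0)/(1.1r))]

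For m1 = 6.8, m0 = 7.1, r = 0.5, q = 0.28:
- observed part: 0.572 − 0.464 = 0.108
- imputed part: 0.642 − 0.428 = 0.214
- total: 0.72 × 0.108 + 0.28 × 0.214 = 0.138, or 13.8 points against a true 10.8

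| Means | True | 28% missing, r = 0.3 / 0.5 / 0.7 | 10% missing, r = 0.3 / 0.5 / 0.7 |
|---|---|---|---|
| 6.8 / 7.1 | 10.8 | 17.5 / 13.8 / 12.1 | 13.2 / 11.9 / 11.3 |
| 6.5 / 6.8 | 10.3 | 13.2 / 12.4 / 11.3 | 11.4 / 11.0 / 10.7 |
| 6.0 / 6.3 | 8.1 | 6.2 / 7.7 / 8.2 | 7.4 / 7.9 / 8.1 |

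The simulation with baseline in the model gives 16.8 / 13.7 / 12.1 for the first row with 28% missing.

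**The case against.** The strongest reply is that the specific rule overrides the general one. Section 5.12.2.3 names the endpoint, estimand, data set and imputation model, so a programmer would follow it. That is probably right, and it reduces the conflict with 5.12 to a missing exception. It does not supply the draw method or the combining rule, and the section names both multiple imputation and Rubin's rules only for the other estimand.

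The departure from the protocol's exclusion rule is not an error in itself. Protocol 10.3.1 and SAP 5.2 let the SAP change methods that are not a principal feature. This stands.

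Several limits on the size also stand:
- The worst figures occur at correlation 0.3. A full MMRM uses all earlier on-treatment visits and may predict better than the single last value used here.
- The different calls depend on the effect size. With means 6.5 and 7.0 and 28% missing, the methods disagreed in at most 0.2% of 400 trials.
- 28% is a planning ceiling.
- Rescue is triggered by high glucose or HbA1c, so assuming unrelated dropout flatters exclusion.
- Multiple imputation is somewhat conservative here. Specifying exclusion would also end the ambiguity.

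At a larger effect the significance call settles, but the interval and the responder difference still depend on the unstated choice.

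**Conclusion.** The concern holds and should be fixed. The SAP contradicts itself on whether to impute, and the section that imputes does not define a valid analysis for this estimand.

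The harms rest on different conditions. The effect on significance calls arises under any reading of 5.12.2.3, at a true difference near 0.30. Intervals that are too narrow arise only if it is run as single imputation. Distortion of the responder difference arises only with predicted values, and its size and sign depend on the assumed means and correlation. The sizes are illustrative, since they rest on the assumptions listed above.

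Family-wise error failure is not alleged. The primary analysis and the treatment-regimen analysis of this endpoint are unaffected.

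**What to change.** - **SAP 5.12.2.3:** state that missing Week 52 HbA1c is multiply imputed from the stated MMRM with both parameter and residual uncertainty, and give the number of imputations. Dichotomise each completed dataset at 7%, fit the stated logistic model to each, and combine by Rubin's rules. Name this as the test that enters 5.12.3, and label the longitudinal logistic model supportive.
- **SAP 5.12:** list 5.12.2.3 as an exception to the no-imputation rule.
- **SAP 5.4:** limit the reference to 5.12.1.3 to the treatment-regimen estimand.

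The cost is SAP wording and a little programming, since the combining step is already needed for the treatment-regimen estimand. Intervals will be wider than with single imputation. Power in these runs stayed at or above that of exclusion (74–88% against 71–82% with 28% missing and a difference of 0.30).
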